APPENDIX I-B: Schedule of Procedures and Evaluations - Safety Phase*

Procedures/Evaluations	Screening Visit	Enrollment/ Randomization Visit	Week 1	Week 2	Week 3	Week 4
Screening Informed Consent	X					
Enrollment Informed Consent ¹		X				
Demographics	X					
Locator Information	X	X				X
Eligibility Interview (incl. DSM-IV diagnosis)	X					
Behavioral Risk Assessment (drug use and sexual risk)	X					
Social Harms Assessment			X	X	X	X
Physical Examination for HIV negative pts.	X					
Symptom-directed Physical Exam			X	X	X	X
Intervention Acceptability Assessment						X
Targeted Medical history for HIV negative pts.	X					
Interim Medical History			X	X	X	X
Randomization		X				
Laboratory Tests						
Rapid HIV testing ²	X					
Hepatitis B & C ³	X					
Platelet count	X		X	X	X	X
CBC	X		X	X	X	X
Bilirubin	X		X	X	X	X
Creatinine	X		X	X	X	X
ALT	X		X	X	X	X
Urine Test for Opiates and other drugs	X		X	X	X	X
Urine Test for Pregnancy ⁴	X	X				X
Pre- and Post-test HIV Counseling	X					
Counseling Visits			X	X	X	X
BUP/NX Dispensing Visits ⁵		X	X	X	X	X

¹Participants will provide consent for study enrollment on or before the visit at which they are randomized.

NOTE: The first 50 participants enrolled at each site will undergo the same screening and randomization procedures as participants enrolled later in the study; however, more safety data will be collected during the first month of enrollment. These participants will continue on the same schedule of activities after the first month as all other enrollees, as described in Appendix I-A.

[figure not shown]
²If positive, confirmatory testing to be performed according to the algorithm in Appendix II-A.

³After screening, hepatitis testing may be performed at any point during first year of participation if clinically indicated. Hep B vaccine will be offered to randomized participants if appropriate.

[figure not shown]
4For female participants only.

⁵Completed daily for up to the first three weeks of dosing in both arms, and three times per week thereafter in the substitution arm.

APPENDIX II-A: HIV Antibody Testing Algorithm - Screening

determine HIV infection status

APPENDIX IV: Referral Information for Sites

Please provide the requested information for each health care facility or organization that your site has used or will use for referrals for participants who are screened for or enrolled in the HPTN 058 protocol. Examples of organizations that you might use for referrals are support groups, emergency shelters, needle exchanges, medical care for HIV, and so on. This list should be updated at least every six months and will be monitored during site visits by sponsor representatives.

a.	Name of organization and contact person at this organization:
b.	Address and phone number of organization:
c.	Types of services/care provided at this organization and the cost of each:
d.	Approximate distance of organization from your research site:
e.	Days/hours when services are available:
f.	Typically, how long does it take to get an appointment at this organization?
g.	Has anyone from your research site visited this organization in the last six months?
h.	Has your research site or your research participants experienced any problems or challenges with this referral site? If yes, please describe.

Referral List for [name of site]

Organization	Address/Phone	Contact Person	Types of services offered and cost of each	Info last updated

This list will be used by HPTN staff when making referrals for participants who are screened for or enrolled in HPTN 058. This list should be updated regularly.

APPENDIX V: Equipoise in HPTN 058: Comparisons between the Two Study Arms

The following table is designed to summarize efficacy rates for key outcomes described in the available literature and individual and community level risks and benefits in each arm. As the table demonstrates, though efficacy for reduction in opiate use is not expected to be high in the detoxification treatment arm, efficacy for reduction in HIV incidence may be higher than hypothesized in the protocol given the available data demonstrating that behavioral interventions can dramatically reduce HIV risk behaviors. Additionally, the table illustrates that risks and benefits for participants in both arms are generally similar.

	Detoxification and Counseling Arm	Substitution and Counseling Arm		
Efficacy information from available literature:				
HIV incidence HIV in		No studies have been conducted examining HIV incidence during or following buprenorphine treatment. Observational studies of self-selected subjects have found significant associations between retention in methadone maintenance and lower rates of HIV incidence. See Section 1.1.1 for more information.		
Opiate Use	Long-tem outcomes and relapse rates from rapid opiate detoxification with buprenorphine followed by counseling have not been reported. It appears that buprenorphine is as effective as methadone for detoxification, though brief detoxification alone is unlikely to result in long-term abstinence from opiate use.	Several clinical trials have firmly established the efficacy of buprenorphine compared to placebo for reduction of opiate use. The percentage of participants in these trials with consistently opiate negative urine samples has ranged broadly based on length of treatment and dose. See Section 1.1.3 for more information about the efficacy of BUP/NX in the treatment of opiate use.		
Needle Sharing	Studies show an average 27% reduction in needle sharing at 6-months among injectors exposed to behavioral interventions. See Section 1.1.1.	50-80% reduction based upon observational studies of methadone patients relative to untreated injectors.		
Benefits to individuals screened for HPTN 058	 HIV, HBV, & HCV counseling and testing Referral to available community health care for identified medical problems If HIV positive, referral to available HIV services in the community Referral to available drug treatment services in the community 			
Benefits to individuals enrolled in HPTN 058	 HIV counseling and testing every 6 months and on demand between assessment intervals HBV and HCV testing as clinically indicated Hepatitis B vaccine offered if appropriate Outpatient BUP/NX detoxification during first 2-3 weeks of study Weekly drug and risk reduction counseling during first 3 months of study Monthly drug and risk counseling during months 4 through 12 of study Referral to available community health care for identified medical problems If HIV positive, referral to available HIV 	 HIV counseling and testing every 6 months and on demand between assessment intervals HBV and HCV testing as clinically indicated Hepatitis B vaccine offered if appropriate Outpatient BUP/NX maintenance during first year of study Weekly drug and risk reduction counseling during first 3 months of study Monthly drug and risk counseling during months 4 through 12 of study Referral to available community health care for identified medical problems If HIV positive, referral to available HIV 		

	services in the community Referral to available drug treatment services in the community No potential interaction with other (e.g., HIV) drugs after detoxification phase	services in the community Referral to available drug treatment services in the community Withdrawal easily tolerated during taper phase	
Risks to individual participants	 Potential unwanted disclosure of drug use status as a result of participating in study procedures Potential distress caused by discussions of drug use and related risks Potential for rapid return to drug use following treatment phase Treatment participation (weekly and monthly counseling sessions) may interfere with work or social activities Discomfort during detoxification Medication side effects during detoxification phase 	 Potential unwanted disclosure of drug use status as a result of participating in study procedures Potential distress caused by discussions of drug use and related risks Potential for rapid return to drug use following treatment phase Treatment participation (3 times per week medication visits and counseling visits) may interfere with work or social activities Discomfort during induction phase Medication side effects during year of administration Discomfort during taper (end of treatment titration) phase 	
Benefits/ advantages to community/ region	 Increased number of professionals able to deliver drug and risk-reduction counseling and train others Increased number of physicians able to prescribe buprenorphine and train others Improved data regarding HIV prevalence and incidence Improved infrastructure (laboratory, pharmacy, etc) Increased understanding of drug use and related HIV and HCV infection rates Possible reduced spread of HIV to IDUs and other populations Individual drug and risk counseling manuals (translated for use in Thailand and China and possibly others) Buprenorphine administration manuals (translated for use in Thailand, and China and possibly others) Data to inform policy makers on the impact of detoxification and counseling (low intensity) relative to one year of BUP/NX treatment (high intensity) Increased opportunities for regional and international collaborations and networking 		
Risks/ disadvantages to community/ region	 More expensive than methadone Small risk of BUP/NX diversion to street use Study may prove inconclusive May conflict with country policies 		

APPENDIX VI: HPTN 058 Adverse Event Reporting and Documentation Requirements*

	Adverse Event	RELATIONSHIP TO STUDY PRODUCT	Record event and grade in primary source documents	AE LOG (DataFax to SDMC)	EAE FORM (to DAIDS RCC within 3 business days of site awareness)
	Results in Death	Regardless of relationship	YES	YES	YES
	Results in persistent or significant disability or incapacity	Regardless of relationship	YES	YES	YES
	Is a congenital anomaly or birth defect or fetal loss	Regardless of relationship	YES	YES	YES
Serious Adverse Events	Requires or prolongs hospitalization	Probably not related Possibly related Probably related Definitely related	YES	YES	YES (if meets one of the relationship criteria)
	Requires intervention to prevent significant incapacity/permanent disability or death	Probably not related Possibly related Probably related Definitely related	YES	YES	YES (if meets one of the relationship criteria)
	Is life-threatening (including all Grade 4 AEs)	Probably not related Possibly related Probably related Definitely related	YES	YES	YES (if meets one of the relationship criteria)
	All other SAEs	Not related to study product	YES	YES	NO (unless directly related to study participation)
Non- Serious Adverse Events	All non-serious AEs	Regardless of relationship	YES	NO	NO

^{*} All AEs must be documented in the participant's source record, regardless of seriousness, severity or relatedness. AEs will only be documented and reported to the SDMC/DAIDS as appropriate for participants in both study arms through week 52 of follow-up.

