3.2.1 Women and Contraception

BUP/NX is a pregnancy Category C drug. The effects of it on fetal development have not been comprehensively studied; therefore a woman may enroll in the study only if she is unable to become pregnant or is using, or willing to use, an acceptable method of contraception for the first twelve months of the study. Available contraception in the study sites may vary, but acceptable options include, but are not limited to, hormonal methods, barrier methods (diaphragm or condom), and intrauterine devices, and complete abstinence from sexual intercourse. Women who report that they are abstinent will be counseled about contraceptive options and asked if they are willing to use an effective method of birth control in the event that they become sexually active. Male condoms will be offered at the study sites along with referrals to family planning providers. If a participant becomes pregnant during the trial and is on study drug, she will continue to be followed as a study participant but will be tapered gradually from BUP/NX and referred for appropriate care. Pregnant women will also be counseled about the risks and benefits of drug treatment during pregnancy and will be provided with referrals for alternative treatment options including methadone and buprenorphine (without naloxone) when available. Pregnancy outcomes will be ascertained from the participant by verbal report when possible.

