4.4.2 Considerations for Women who Become Pregnant during the Study

BUP/NX is a pregnancy Category C drug. High doses of buprenorphine can pass through breast milk. Therefore, women who are pregnant or lactating are excluded from enrollment. During the informed consent process, local site staff will discuss the available data on BUP/NX and pregnancy with female study volunteers. Given the limited data on the safety of BUP/NX use throughout pregnancy, women who become pregnant will be discontinued from BUP/NX, with gradual tapering, for the duration of their pregnancy. Pregnant women will also be counseled about the risks and benefits of drug treatment during pregnancy and will be provided with referrals for alternative treatment options including methadone and buprenorphine alone when available.

Urine pregnancy tests will be performed approximately every four weeks during BUP/NX treatment. Pregnant women will be maintained in follow-up to ascertain study endpoint information. Clinical status of infants born to women who become pregnant while taking BUP/NX will be obtained by interview of the woman after delivery; if a woman withdraws from the study prior to completion of her pregnancy, every effort will be made to obtain this information. Reporting of fetal losses will follow DAIDS adverse event (AE) reporting requirements. Resumption of BUP/NX in women who have pregnancy losses, either spontaneous or elective, will follow the same procedures as those outlined in Section 3.5.1.

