Specifically, the 'standard' level of reporting defined in the DAIDS EAE manual will be followed for the first 52 weeks of follow-up for participants in both study arms (from study enrollment until the participant completes 52 weeks of follow-up or is terminated from study participation for any reason). Conditions and illnesses identified in participants prior to randomization will be considered pre-existing conditions and will not be reported as adverse events, unless the condition worsens after randomization (increases in severity or frequency), in which case it would be reported as an AE.

The study drug in HPTN 058 is the BUP/NX combination (Suboxone), provided for 52 weeks to participants randomized to the substitution arm and, for participants randomized to the detoxification arm, up to 18 days beginning at randomization and/or within 30 days of the six month visit; therefore it is the relationship of all AEs to this product that is to be considered in determining the reporting requirements for each AE (e.g., whether the AE must be reported in an expedited manner to DAIDS).

All adverse events occurring in participants through week 52 will be graded according to the DAIDS Table for Grading the Severity of Adult and Pediatric Adverse Events, dated December 2004, which will be included in the SSP Manual and is available at the following website: http://rcc.tech-res-intl.com. All serious adverse events (SAEs), regardless of severity or relatedness, and all AEs that otherwise meet the criteria for expedited reporting to DAIDS (EAEs) occurring to participants in either study arm through week 52 will be reported on a standard AE DataFax case report form for entry into the study database. AEs that are not serious or do not otherwise meet the criteria for expedited reporting to DAIDS will be recorded in the study source documentation but will not be included in the study database. As noted above, for the purposes of this study, outpatient or inpatient hospital/medical facility admission for drug addiction treatment or rehabilitation will not be considered a serious adverse event.

There will be no active reporting of adverse events after the period specified above (52 weeks of follow-up); however, unexpected, serious adverse drug reactions must be reported if the study site staff become aware of the events on a passive basis, i.e., from publicly available information.

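### Active adverse event reporting stops at week 52 with no exception for pregnancy outcomes, yet most births conceived on BUP/NX in the substitution arm would come later

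*Protocol*

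**What the plan says.** Appendix VI has a row among the serious adverse events labelled "Is a congenital anomaly or birth defect or fetal loss". It calls for an entry in the source record, on the AE log sent to the SDMC and on the expedited form to DAIDS, regardless of relationship to study product. The footnote to that table sets the time limit: "AEs will only be documented and reported to the SDMC/DAIDS as appropriate for participants in both study arms through week 52 of follow-up".

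Section 6.2 agrees. Serious and expedited events "occurring to participants in either study arm through week 52 will be reported on a standard AE DataFax case report form", and active reporting stops after 52 weeks of follow-up. One later duty remains: "unexpected, serious adverse drug reactions must be reported if the study site staff become aware of the events on a passive basis". The section explains passive awareness as learning of the event from sources open to the public.

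Section 4.4.2 looks further ahead: "Clinical status of infants born to women who become pregnant while taking BUP/NX will be obtained by interview of the woman after delivery". It sets no week limit, asks for every effort even if the woman withdraws before the pregnancy ends, and sends fetal losses to the DAIDS AE reporting requirements. Section 3.2.1 is softer: "Pregnancy outcomes will be ascertained from the participant by verbal report when possible". On the drug itself, that section gives pregnancy Category C and adds: "The effects of it on fetal development have not been comprehensively studied".

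Under Section 3.5.1 nobody receives BUP/NX beyond 52 weeks from enrollment, so in the substitution arm dosing and active reporting can end together.

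**The concern.** A birth outcome appears months after the exposure that might have affected it. A reporting window that closes with the last dose therefore misses many outcomes of pregnancies that began on drug. The protocol asks sites to find out about these infants and ranks an anomaly among the events that are always reportable. Its time limit then leaves a late one without a clear path to the SDMC or DAIDS.

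This is about exposure during treatment whose result must come late. It is not a complaint that events arising in the off-drug year go unreported.

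Two things are at stake. Section 6.2 builds the annual reports to the FDA from adverse events in the study database, so an unreported outcome would be absent there too. And the pregnancy data that do reach the database would be weighted towards conceptions early in treatment and towards losses, which end sooner than births.

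**Working it through.** The protocol gives no figure for pregnancy outcomes, so there is none to reproduce. The check asks what share of pregnancies conceived on BUP/NX would end after week 52.

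**Inputs from the protocol**
- Reporting window: enrollment to week 52 (Section 6.2, Appendix VI).
- Substitution-arm exposure: up to week 52 (Section 3.5.1).
- Detoxification arm: at most 18 days per course (Section 4.3.3), with an optional second course at about week 26.
- Women are tested as not pregnant at first dosing (Section 5.2), so on-drug conceptions begin at about week 0.
- Minimum follow-up: 104 weeks (Section 2.3).

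**Assumptions, not in the protocol**
- Time *g* from conception to outcome: 38 weeks for a term birth (range 34–40) and 6–20 weeks for a fetal loss.
- A constant chance of conception while on drug.

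**Formula.** An outcome falls after week 52 if conception comes after week 52 − *g*. With everyone on drug for the full year, the share is *g*/52.

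| Outcome | *g* (weeks) | Share after week 52 |
|---|---|---|
| Birth | 34 | 34/52 = 65% |
| Birth | 38 | 38/52 = 73% |
| Birth | 40 | 40/52 = 77% |
| Fetal loss | 6 | 6/52 = 12% |
| Fetal loss | 12 | 12/52 = 23% |
| Fetal loss | 20 | 20/52 = 38% |

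At 38 weeks, only conceptions before week 52 − 38 = 14 deliver inside the window.

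**Falling retention.** If the proportion on drug declines linearly by *d* over the year, exposure after week 14 is 38 − *d*(52² − 14²)/104 = 38 − 24.12*d*, out of a total of 52 − 26*d*.
- *d* = 0.25 (75% still on drug at week 52): 31.97/45.5 = 70%.
- *d* = 0.50: 25.94/39 = 67%.
- *d* = 0.75: 19.91/32.5 = 61%.

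Varying one factor at a time gives 61–77%. Combining the shortest gestation (34 weeks) with the steepest decline (*d* = 0.75) gives 52%. Under exponential discontinuation at *g* = 38, the share falls below one half only if about 11% or fewer are still on drug at week 52.

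**Detoxification arm.** The first course ends by 18/7 = 2.6 weeks, so a term birth after conception on it comes by 2.6 + 38, about week 41, inside the window. Conception at the second course gives 26 + 38 = week 64, outside it. Adding this arm's exposure to the substitution arm's gives about 67–71% at 38 weeks.

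**All pregnancies together.** If 10–40% end in loss at 10 weeks, the share ending after week 52 runs from 0.10 × 10/52 + 0.90 × 38/52 = 68% down to 0.40 × 10/52 + 0.60 × 38/52 = 52%.

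**Could the late outcomes be learned?** Conception at week 52 reaches term at about 52 + 38 = week 90, inside the 104-week minimum follow-up.

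**The case against.** The strongest reply is that Section 4.4.2 governs collection while Section 6.2 and Appendix VI govern reporting, so the interface is unclear rather than contradictory. Much else limits the damage:

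- The Appendix VI footnote still requires every adverse event in the source record.
- Sections 6.2 and 8.1 keep reporting to IRBs and ethics committees, including unanticipated problems, with no week-52 limit on those sentences.
- Section 6.2 relies on the DAIDS EAE Manual, which is not shown and may have pregnancy rules. The case report forms are not shown either.
- Entry requires women to be unable to conceive or willing to use contraception for twelve months, and pregnancy outcome is not an efficacy endpoint.

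All of this stands, and it rules out some stronger readings. A reader might infer that these outcomes never reach the database. That goes too far: births conceived before about week 14 fall inside the window, as do about 62–88% of fetal losses. A reader might also take the passive route to be the only one left. Ethics committee reporting shows otherwise. Nor does the protocol call fetal harm a known risk; it says the effects have not been fully studied.

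The reply does not close the gap to the SDMC and DAIDS. The passive duty covers unexpected serious drug reactions, whereas Appendix VI requires birth defects to be reported regardless of relationship. A planned interview is not clearly passive awareness from public sources. As for the Manual, Section 6.2 itself applies its standard reporting level only to the first 52 weeks.

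**Conclusion.** The point holds as a mismatch between a required post-delivery interview and a reporting limit that makes no allowance for it. About 60–77% of births conceived on BUP/NX in the substitution arm would fall after week 52, given 34 to 40 weeks to birth and a constant chance of conception on drug. The worst combination tried gives 52%. For those births an anomaly found at interview has no clear active route to the study database or to DAIDS.

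The word *most* applies to births only; for fetal losses the late share is about 12–38%. The percentages describe timing, not counts: the number of women is not given, and the pregnancies affected may be few. No efficacy conclusion is touched. It is still worth correcting, because the protocol itself treats each such event as always reportable and the correction is cheap.

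**What to change.** Reconcile Section 4.4.2 with Section 6.2 and Appendix VI. Add one sentence to Section 6.2 and one to the Appendix VI footnote, to this effect: for a pregnancy conceived while the woman was receiving BUP/NX, in either arm, a congenital anomaly, birth defect or fetal loss is recorded on the AE log and reported as Appendix VI sets out, whenever the pregnancy ends within study follow-up or the outcome is learned through the Section 4.4.2 interview.

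The interview, the log and the expedited form already exist, and no dosing or clinical rule changes. The cost is two sentences and a few forms arriving after week 52.
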